7.3.1. Summaries of Numeric Laboratory Results

Descriptive statistics will be provided by treatment group for each laboratory test specified in the study protocol as follows:

- Baseline values
- Values at each postbaseline analysis window
- Change and percentage change from baseline each postbaseline analysis window (if specified).

A baseline laboratory value will be defined as the last measurement obtained on or prior to the date/time of first dose of study drug. Change from baseline to a postbaseline visit will be defined as the visit value minus the baseline value. The mean, median, Q1, Q3, minimum, and maximum values will be displayed to the reported number of digits; SD values will be displayed to the reported number of digits plus 1.

Median (Q1, Q3) of the observed and change from baseline values for specified laboratory tests will be plotted using a line plot by treatment group and visit.

In the case of multiple values in an analysis window, data will be selected for analysis as described in Section 3.7.4.

7.3.2. Graded Laboratory Values

The DAIDS Toxicity Grading Scale, Version 2.1 will be used to assign toxicity grades (0 to 4) to laboratory results for analysis. Grade 0 includes all values that do not meet the criteria for an abnormality of at least Grade 1. For laboratory tests with criteria for both increased and decreased levels, analyses for each direction (ie, increased, decreased) will be presented separately.

7.3.2.1. Treatment-Emergent Laboratory Abnormalities

Treatment-emergent laboratory abnormalities are defined as values that increase at least 1 toxicity grade from baseline at any time after baseline and up to and including the date of last dose of study drug plus 30 days, will be summarized. The incidence of treatment-emergent laboratory abnormalities and Grade 3 and 4 laboratory abnormalities will also be summarized. If baseline data are missing, any graded abnormality (ie, at least a Grade 1) will be considered treatment emergent). The maximum postbaseline toxicity grade will be summarized by laboratory parameter.

7.3.2.2. Summaries of Laboratory Abnormalities

Laboratory data that are categorical will be summarized using the number and percentage of participants in the study with the given response at baseline and each scheduled postbaseline visit. Participants will be categorized according to the most severe postbaseline abnormality grade for a given lab test.

The following summaries (number and percentage of participants) for treatment-emergent laboratory abnormalities will be provided by lab test and treatment group:

- Graded treatment-emergent laboratory abnormalities during the study (ie, through Week 24)
- Graded treatment-emergent laboratory abnormalities through Week 12
- Grade 3 and 4 treatment-emergent laboratory abnormalities during the study (ie, through Week 24)

- Grade 3 and 4 treatment-emergent laboratory abnormalities through Week 12.

For all summaries of laboratory abnormalities, the denominator is the number of participants with nonmissing postbaseline values during the time period specified in Section 7.2.

Laboratory abnormalities that occur before the first dose of study drug or after the participant has been discontinued from treatment for at least 30 days will be included in a data listing. Treatment-emergent laboratory abnormalities will be flagged.

A by-participant listing of treatment-emergent Grade 3 or 4 laboratory abnormalities will be provided by participant ID number and visit in chronological order. This listing will include all test results that were collected throughout the study for the lab test of interest, with all applicable severity grades abnormal flags displayed.

7.3.3. Metabolic Laboratory Evaluations

For metabolic assessments, including fasting glucose and the lipid panel (ie, total cholesterol, triglycerides, LDL, HDL, total cholesterol to HDL ratio), only those measurements under fasting status will be summarized.

Median (Q1, Q3) of change from baseline in fasting metabolic assessments over time will be plotted by treatment group.

7.3.4. Liver-related Laboratory Evaluations

Liver-related abnormalities after initial study drug dosing will be examined and summarized using the number and percentage of participants who were reported to have the following laboratory test values for (1) postbaseline measurements through Week 12 and (2) postbaseline measurements during the study (ie, through Week 24):

- Aspartate aminotransferase (AST): (a) > 3 times of the upper limit of reference range (ULN); (b) $> 5 \times$ ULN; (c) $> 10 \times$ ULN; (d) $> 20 \times$ ULN
- Alanine aminotransferase (ALT): (a) $> 3 \times$ ULN; (b) $> 5 \times$ ULN; (c) $> 10 \times$ ULN; (d) $> 20 \times$ ULN
- AST or ALT: (a) $> 3 \times$ ULN; (b) $> 5 \times$ ULN; (c) $> 10 \times$ ULN; (d) $> 20 \times$ ULN
- Total bilirubin: (a) $> 1 \times$ ULN; (b) $> 2 \times$ ULN
- Alkaline phosphatase (ALP) $> 1.5 \times$ ULN
- AST or ALT $> 3 \times$ ULN and total bilirubin: (a) $> 1.5 \times$ ULN; (b) $> 2 \times$ ULN
- AST or ALT $> 3 \times$ ULN and total bilirubin: $> 2 \times$ ULN and ALP $< 2 \times$ ULN

The summary will include data from all postbaseline visits during the time period specified in Section 7.2. For individual laboratory tests, participants will be counted once based on the most severe postbaseline values. For both the composite endpoint of AST or ALT and total bilirubin, participants will be counted once when the criteria are met at the same postbaseline visit date. The denominator is the number of participants in the Safety Analysis Set who have nonmissing postbaseline values of all relevant tests at the same postbaseline visit date. A listing of participants who met at least 1 of the above criteria will be provided.

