### 4.2. Inclusion Criteria

Participants must meet all of the following inclusion criteria to be eligible for participation in this study:

- 1) Participants 18 years of age or older and able to understand and give written informed consent.
- 2) PWH or provider decision to switch off CAB+RPV IM injections due to intolerance, inconvenience, AEs, *or* willing to switch to (and intention to remain on) daily B/F/TAF.
- 3) Currently virologically suppressed (HIV-1 RNA < 50 copies/mL) on CAB+RPV IM injections (Q2M).
- 4) Currently on CAB+RPV IM injections (Q2M) and received at least one dose of CAB+RPV IM injection; no missed CAB+RPV injections
- 5) Ability to receive B/F/TAF up to 7 days prior to the next scheduled dose of CAB+RPV.
- 6) Documented plasma HIV-1 RNA < 50 copies/mL during treatment for  $\geq$  6 months preceding the screening visit.
  - a) Unconfirmed HIV-1 RNA  $\geq$  50 copies/mL (transient detectable viremia, or “blip”) prior to screening are acceptable.
  - b) If the lower limit of detection of the local HIV-1 RNA assay is < 50 copies/mL (eg, < 20 copies/mL), the HIV-1 RNA level cannot exceed 50 copies/mL on 2 consecutive visits.

7) Adequate renal function

Estimated GFR  $\geq 30$  mL/min according to the Cockcroft-Gault formula {Cockcroft 1976} based on serum creatinine and actual body weight as measured at screening and upon admission, eg,

a) Male:

$$\frac{(140 - \text{Age [years]}) \cdot (\text{Weight [kg]})}{72 \cdot (\text{Serum Creatinine [mg/dL]})} = \text{CLcr (mL/min)}$$

b) Female:

$$\frac{(140 - \text{Age [years]}) \cdot (\text{Weight [kg]})}{72 \cdot (\text{Serum Creatinine [mg/dL]})} \times 0.85 = \text{CLcr (mL/min)}$$

8) Participants assigned female at birth of childbearing potential who engage in heterosexual intercourse must agree to use protocol-specified method(s) of contraception as described in Appendix 11.5.

9) Hepatic transaminases (AST and ALT)  $\leq 5 \times$  upper limit of normal (ULN)

10) Total bilirubin  $\leq 1.5$  mg/dL ( $\leq 26$   $\mu$ mol/L), or normal direct bilirubin.

11) No documented or suspected resistance to BIC, FTC, or tenofovir (TFV).

12) Must be willing and able to comply with all study requirements.

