7.1. Safety Endpoints

The co-primary endpoints of this study are:

- Proportion of participants experiencing treatment-emergent Grade 3 or 4 study drug-related adverse events (AEs) through Week 12
- Proportion of participants experiencing treatment-emergent Grade 3 or 4 laboratory abnormalities through Week 12.

The secondary safety endpoints of this study are:

- Proportion of participants experiencing treatment-emergent Grade 3 or 4 study drug-related adverse events (AEs) through Week 24
- Proportion of participants experiencing treatment-emergent grade 3 or 4 laboratory abnormalities through Week 24.

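### The liver-threshold table in SAP 7.3.4 has no baseline reference, so elevations permitted at entry can be counted in nine of its 18 rows, including the transaminase-bilirubin composites

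*SAP*

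**What the plan says.** SAP 7.3.4 plans a table, through Week 12 and through Week 24, introduced as follows: "Liver-related abnormalities after initial study drug dosing will be examined and summarized using the number and percentage of participants". The rows are fixed multiples of ULN for AST, ALT, either transaminase, total bilirubin and ALP, plus three composites of AST or ALT > 3 × ULN with raised bilirubin. For single tests, "participants will be counted once based on the most severe postbaseline values". For the composites, "participants will be counted once when the criteria are met at the same postbaseline visit date". The section excludes no one already above a cut at baseline, requires no rise, and plans no shift table. It adds a listing of participants who meet any criterion, but does not say that the listing shows baseline values.

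Protocol 4.2 sets the entry limits. Criterion 9 allows AST and ALT up to 5 × ULN. Criterion 10 allows total bilirubin up to 1.5 mg/dL, "or normal direct bilirubin", so the second route has no cap on total bilirubin. Neither 4.2 nor 4.3 limits ALP.

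Elsewhere the SAP does refer to baseline. Section 7.3.2.1 defines treatment-emergent laboratory abnormalities as "values that increase at least 1 toxicity grade from baseline at any time after baseline", and 7.3.2.2 tabulates them by laboratory test. The co-primary endpoint in 7.1 uses that definition: "Proportion of participants experiencing treatment-emergent Grade 3 or 4 laboratory abnormalities through Week 12". Section 7.3.1 gives change from baseline for numeric results.

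**The concern.** The entry limits for liver tests lie above some of the cuts used to count liver abnormalities after dosing. A participant whose ALT is 4 × ULN on Day 1 and stays there is counted in the > 3 × ULN row. If that participant also has raised total bilirubin with normal direct bilirubin, the composite criterion can be met on Day 1 and again at each later visit.

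The study has one arm, so there is no comparator rate against which to read the counts. Its rationale (Protocol 1.3) is that data on the combined toxicity of bictegravir and residual cabotegravir are lacking. The composite rows are the ones a reader is most likely to take as a signal of drug injury, and in a study of this size a single count changes how they read. Carry-over is plausible. Criterion 2 admits people leaving CAB+RPV because of adverse events, and although Protocol 4.3 excludes chronic hepatitis B, it names no hepatitis C exclusion.

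**Working it through.** The documents give no figure on this point and made no sample size calculation (SAP 1.3), so there is nothing to reproduce. The check has four steps.

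**1. Which rows can a stable value within the entry limits meet?**

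| SAP 7.3.4 rows | Number of rows | Entry limit | Met by a stable entry value? |
|---|---|---|---|
| AST, ALT, AST or ALT: > 3 × ULN | 3 | ≤ 5 × ULN | Yes, for values above 3 and up to 5 × ULN |
| The same tests: > 5, > 10, > 20 × ULN | 9 | ≤ 5 × ULN | No |
| Total bilirubin > 1 × ULN | 1 | ≤ 1.5 mg/dL, or normal direct bilirubin | Yes, by either route |
| Total bilirubin > 2 × ULN | 1 | As above | Only by the normal-direct-bilirubin route |
| ALP > 1.5 × ULN | 1 | None | Yes |
| AST or ALT > 3 × ULN with bilirubin > 1.5 or > 2 × ULN, and the version with ALP < 2 × ULN | 3 | As above | Yes, by the normal-direct-bilirubin route |

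The bilirubin entries assume a laboratory ULN of 1.0 to 1.4 mg/dL, which the documents do not give. Then 1.5 mg/dL is 1.5/1.0 = 1.5 down to 1.5/1.4 = 1.07 × ULN. That is above 1 × ULN throughout and never above 1.5 × ULN. In total 3 + 2 + 1 + 3 = 9 of 18 rows are open to carry-over.

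**2. Is there a baseline-referenced table elsewhere?** For AST, ALT, bilirubin and ALP as single tests, yes: SAP 7.3.2.1 and 7.3.2.2 (treatment-emergent grades) and 7.3.1 (change from baseline). For the composites, no, because those sections work one laboratory test at a time.

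**3. Size per participant.** Take n = 35, assuming everyone has the relevant post-baseline values, and exact (Clopper-Pearson) limits.
- 0/35 = 0%. Upper limit 1 − 0.025^(1/35) = 10.0%.
- 1/35 = 2.9%. Lower limit 1 − 0.975^(1/35) = 0.07%; upper limit 14.9%.
- 2/35 = 5.7% (0.7 to 19.2%).

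If one participant met a criterion at baseline and no one met it newly, the count among the others would be 0/34, with upper limit 1 − 0.025^(1/34) = 10.3%.

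**4. Chance of any carry-over.** The share p of participants above a given cut at entry is not in the documents, so p is an assumption. Expected number 35p; P(at least one) = 1 − (1 − p)^35.

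| p | Expected | P(at least one) |
|---|---|---|
| 1% | 0.35 | 0.30 |
| 2% | 0.70 | 0.51 |
| 3% | 1.05 | 0.66 |
| 5% | 1.75 | 0.83 |
| 10% | 3.5 | 0.975 |

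For the composites p is likely to be smaller than for a single test, since one person must meet both parts.

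**The case against.** The best defence is that 7.3.4 is a supplementary screen that does what it says. Its word is abnormalities, and a value above 3 × ULN after dosing is one. It claims neither new onset nor causation. Counting every exceedance is the cautious choice for safety. The single tests already have treatment-emergent tables, and SAP 7.3 plans a chronological by-participant listing of all chemistry results. With about 35 participants, any case can be traced to its own baseline. The number carried in may be zero, and the intervals for 0/35 and 1/35 overlap almost entirely.

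Most of this stands, and it rules out three stronger readings that a reader might infer:
- That the plan reports unchanged values as hepatic events caused by treatment. The SAP does not call them events or treatment-emergent.
- That the primary result is contaminated. The co-primary laboratory endpoint requires a rise from baseline.
- That new and carried-in cases cannot be told apart. They can be, from the listings, though not from the table.

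A reader might also conclude that participants already above a cut should be dropped from the row and counted only on reaching a higher cut. That would be unsafe. Bilirubin > 2 × ULN, ALP > 1.5 × ULN and the > 2 × ULN composites have no higher cut, so a participant going from 2.1 to 8 × ULN bilirubin would not be counted as worsened in any bilirubin row.

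The defence does not cover the composites. No planned table gives them a baseline reference, and a reader of the summary table will not usually have the listings to hand.

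**Conclusion.** The point holds as one of interpretability in a supportive safety table. Nine of the 18 rows in SAP 7.3.4 can include a stable elevation that the entry criteria allow, and for the three composites nothing else in the planned tables separates new from carried-in. Each such participant adds 2.9 percentage points at n = 35. How many there will be is unknown, so this is a possible distortion and not a demonstrated one. The conclusion rests on the entry limits as written, on values that do not change after entry, and, for the bilirubin rows, on an assumed ULN of 1.0 to 1.4 mg/dL. Neither the co-primary endpoints nor the higher transaminase rows are in question. The change is worth making because the table has no comparator and the remedy is small.

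**What to change.** Keep the existing count of all post-baseline exceedances in SAP 7.3.4 and add three things:

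1. A baseline column giving the number of participants who met each criterion at baseline. For composites, all parts should be met on the same baseline date, to match the post-baseline rule.
2. For every row, including ALP and the composites, a second count among participants who did not meet that criterion at baseline, with its own denominator stated. Someone with ALT at 4 × ULN on Day 1 whose bilirubin then rises is still counted as new in the composite. The first count minus the second gives the number who met the criterion both before and after dosing. State how a missing baseline is handled; SAP 3.5.1 already treats it as normal for the laboratory abnormality summary.
3. Baseline values in the listing already planned in 7.3.4, so that worsening in participants already above a cut stays visible.

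Do not replace the current count with an exclusion rule. The cost is a few sentences in the SAP and minor programming. Chemistry is already collected at screening and Day 1 (Protocol Table 3), so no new data are needed.

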### 6.3.5. Clinical Laboratory Assessments

The laboratory analyses will be performed at a central laboratory. Blood and urine samples for clinical laboratory assessments will be collected as specified in the Study Procedures Table (Table 3). Participants only need to be fasted on days where lipid or fasting glucose profiling is scheduled. Fasting is defined as 8 hours without food or drink (except water) prior to laboratory draw.

See Table 1 for a summary of the laboratory analytes.

More frequent sampling as well as additional tests may be performed as deemed necessary by the investigator. Note that in the case where clinically significant laboratory test results are a potential reason for discontinuation from the study drug and withdrawal from the study, retesting of the affected parameter(s) should be prompt (within 3 to 7 days, with the exception of mild creatinine elevation, which may be retested 7 to 14 days apart unless clinically indicated) after the investigator has consulted with the Gilead medical monitor (or designee). A decision regarding participant discontinuation should be made after the results from the retest are available (see Section 3.3 for additional information).

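### The combined AST/ALT-plus-bilirubin rows in SAP 7.3.4 omit participants whose two elevations fall on different dates; a windowed count and an any-time count should be added

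*SAP*

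**What the plan says.** SAP Section 7.3.4 reports liver-related values for two periods, through Week 12 and through Week 24. It uses two counting rules.

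- **Single-test rows** (AST, ALT, AST or ALT, total bilirubin, ALP): "For individual laboratory tests, participants will be counted once based on the most severe postbaseline values". The date plays no part.
- **Composite rows**: "participants will be counted once when the criteria are met at the same postbaseline visit date". The SAP words this rule as applying to both composites. I take the word both to refer to the two composite bullets, the second of which adds the ALP condition, so that all three composite rows follow the rule.

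The denominator is limited to members of the Safety Analysis Set "who have nonmissing postbaseline values of all relevant tests at the same postbaseline visit date". On scope, "The summary will include data from all postbaseline visits during the time period specified in Section 7.2", so unscheduled draws are included. In support, "A listing of participants who met at least 1 of the above criteria will be provided". The section gives no time window and no count that ignores the date.

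On sampling, Table 3 of the Protocol puts AST, ALT, ALP and total bilirubin in one chemistry profile. It is drawn at Weeks 4, 12 and 24, at the early study drug discontinuation (ESDD) visit and, where it applies, at the 30-day follow-up. Protocol Section 6.3.5 adds that "retesting of the affected parameter(s) should be prompt (within 3 to 7 days" of the event, but only "in the case where clinically significant laboratory test results are a potential reason for discontinuation from the study drug". The same section leaves more frequent sampling and extra tests to the investigator.

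**The concern.** The composite rows are the only planned rows that join a transaminase rise to a bilirubin rise in the same participant. If AST/ALT is above 3 x ULN at one draw and bilirubin passes its threshold at a later one, and no single draw shows both, the combined row stays empty. Each single-test row meanwhile gains a participant, and the table does not show whether it is the same person.

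At the 1.5 x ULN bilirubin threshold the table helps even less. The single-test bilirubin rows are set at > 1 x and > 2 x ULN, so no single-test row matches that composite.

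The stake is interpretive. Safety is the primary objective, and Protocol Section 1.3 justifies the trial by the lack of data on BIC taken while CAB is still present, including any joint toxicity. In a study of this size a reader will treat no combined elevations and one combined elevation as different messages.

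**Working it through.** The plan states no figure on this point, so there is nothing to reproduce. The check applies the written rule to possible courses and then gives the scale of one omission.

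**Step 1. Spacing of scheduled panels.** SAP Table 3-1 sets Week 4 at Day 28, Week 12 at Day 84 and Week 24 at Day 168. The gaps are 84 - 28 = 56 days and 168 - 84 = 84 days.

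**Step 2. The rule applied to six invented courses.** All start with ALT 4 x ULN on Day 28. Except in A, bilirubin that day is 1.2 x ULN. The composite is AST or ALT > 3 x ULN with total bilirubin > 2 x ULN. The 30-day column counts bilirubin on the same date as, or up to 30 days after, a qualifying ALT.

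| Course | Later values (x ULN) | Same date | 30-day | Any time |
|---|---|---|---|---|
| A | none needed; bilirubin 2.3 on Day 28 | yes | yes | yes |
| B | Day 35 full panel: ALT 3.5, bilirubin 2.3 | yes | yes | yes |
| C | Day 35 full panel: ALT 2.5, bilirubin 2.3 | no | yes | yes |
| D | Day 33 ALT only 4; Day 40 bilirubin only 2.3 | no | yes | yes |
| E | Day 84 panel: ALT 3.2, bilirubin 2.3 | yes | yes | yes |
| F | Day 84 panel: ALT 1.5, bilirubin 2.3 | no | no | yes |

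Of the five courses with a delayed bilirubin rise (B to F), the same-date rule counts two (B, E) and omits three (C, D, F). The 30-day count recovers C (35 - 28 = 7 days) and D (40 - 28 = 12 days) but not F (84 - 28 = 56 days). The any-time count recovers all three. All six courses enter the single-test ALT row, the single-test bilirubin row and the listing. These tallies show how the rule works; they are not rates.

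**Step 3. Cause.** C and F are omitted although every draw was a full panel. The cause is that the two elevations do not overlap on one date. A missing component matters only in D.

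**Step 4. Direction.** Every participant who meets the criteria on one date also meets the windowed and any-time criteria. The same-date count can therefore equal the other two or fall below them, but cannot exceed them.

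**Step 5. Scale.** N is about 35 (Protocol 8.9, SAP 1.3).

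- With the case counted: 1/35 = 2.9%. Exact 95% limits: lower 1 - 0.975^(1/35) = 0.07%, upper 14.9%.
- With the case omitted: 0/35 = 0%. Exact upper limit 1 - 0.025^(1/35) = 10.0%.

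The SAP plans no confidence intervals for these rows; the limits only show scale.

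**The case against.** The best defence is that same-date concurrence is a pre-specified choice in favour of specificity, and that nothing is hidden. Each such participant is in the single-test rows and in a by-participant listing that, with about 35 people in one arm, can be read case by case. Anyone who stops study drug is due a full panel at the ESDD visit, within 72 hours of the last dose. All of this stands, and it limits the weight of the point. It does not change the combined count, which is the figure most likely to be cited.

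Four stronger readings are tempting, and the documents do not support them.

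- *Single-parameter retests are the main cause.* The retest clause is conditional, allows for more than one parameter, and sits beside a general permission for extra tests. A retest of ALT alone would also yield no bilirubin value for any rule to recover.
- *A later bilirubin rise is always reported as zero cases.* It is counted whenever AST/ALT is still > 3 x ULN on that date (courses B and E).
- *This is the trial's only summary of hepatic injury.* The same section counts AST/ALT up to > 20 x ULN and bilirubin > 2 x ULN at worst value. SAP 7.3.2 covers graded laboratory abnormalities, and SAP 7.2.7 covers Grade 3 or higher, serious and discontinuation-related events.
- *The same-date denominator is itself harmful.* One complete post-baseline panel qualifies a participant, and each scheduled panel holds all the components.

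A 30-day window can also be criticised: it has no direct source in the documents and misses a rise first seen at the next scheduled visit. That is correct, and it is why an any-time count should go with it.

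**Conclusion.** The point holds in a limited form. The composite rows omit participants whose AST/ALT and bilirubin elevations fall on different dates, and the error runs in one direction only. One omitted participant moves the row from 2.9% to 0%. How often this would happen cannot be derived from the documents and is not claimed here.

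The rows are supportive. The co-primary laboratory endpoint, Grade 3 or 4 abnormalities through Week 12, does not depend on them. The change is worth making because it is cheap and the trial exists to describe safety during an unstudied overlap. The conclusion rests on reading the same-date rule as covering all three composites, and on the elevations being able to occur on separate draws, which panels 56 and 84 days apart allow.

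**What to change.** In SAP 7.3.4 keep the same-date rows and add two rows for each of the three composites:

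1. **Windowed:** total bilirubin above threshold on the same date as, or within 30 days after, an AST or ALT value > 3 x ULN.
2. **Any time:** both criteria met at worst post-baseline values up to last dose plus 30 days, whatever the dates. This catches a bilirubin rise first seen at the next scheduled visit.

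For the version through Week 12, all values must fall inside that period. For the ALP composite, use the ALP value from the same draw as the qualifying AST/ALT value or, if there is none, the closest value within 30 days. The denominator for the added rows is participants with at least one post-baseline value of each component. State in the SAP that the 30-day window is an assumption, chosen to match the 30-day safety data period.

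The cost is a paragraph of SAP text and 3 x 2 = 6 extra rows per reporting period, from data already collected and with no change to trial procedures. SAP Section 1 places finalization of the SAP before database finalization, so the change belongs before that point, with an entry in the SAP revision table. The downside is that an unrelated bilirubin rise may be counted, more readily in the any-time row. The planned listing lets the reader resolve such a case.
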